4.2. Scientific Rationale for Study Design

The results from study BEL114055 (Section 2.2.1) are consistent with a positive risk benefit of IV belimumab 10 mg/kg for the treatment of SLE in pediatric population from

5 to 17 years of age and are consistent also with the positive risk benefit of belimumab IV and SC formulations in the adult population. This study aims to confirm that belimumab SC formulation in the pediatric study population has consistent PK and safety profile with belimumab in adult population, and with IV belimumab in pediatric population.

The study is to support the use of belimumab SC in the pediatric population, thereby providing treatment options and allowing patients the potential to administer their medication at home, and decreasing the burden of visits to an infusion center.

The 12-week open-label PK, safety, and PD study of SC belimumab will be followed by an optional open-label 40-week continuation phase. The open-label trial design, in combination with a partial PK extrapolation strategy, is expected to provide longer term data on belimumab SC formulation in this trial population.

4.3. Justification for Dose

The dose and dosing regimens selected for SC administration in this pediatric population are intended to achieve a similar average exposure as observed with the weekly 200 mg SC dosing regimen in adult SLE patients, estimated at 104 μ g/mL from a population PK analysis of SC study data in adults [GSK Document Number [2015N263802_01](#)].

For a fixed belimumab dose the exposure increases as body weight decreases, as observed in adults and supported by the population PK model developed from the pediatric IV study BEL114055. To accommodate children between the ages of 5 to 17, specifically to ensure lower body weight subjects are not over-exposed, three belimumab SC dose groups are proposed and defined by body weight. Pediatric subjects weighing 50 kg or more will receive 200 mg belimumab once a week (QW), as per the recommended dosing regimen in adults. Pediatric participants who weigh between 30 to 50 kg will receive as 200 mg belimumab administered once every ten days (Q10d). Pediatric participants weighing less than 30 kg will receive 200 mg belimumab once every two weeks (Q2W).

The proposed 30 and 50 kg weight thresholds approximately correspond to the age groups 5-9 years, 9-14 years, and 14 years or older - according to the CDC growth chart 9.3 and 14.2-year-old girls have median weights of 30.1 and 50.0 kg, respectively. [https://www.cdc.gov/growthcharts/clinical_charts.htm#Set1].

[figure not shown]
The pediatric population PK model for IV administration, developed from the pediatric IV study data (BEL114055 CSR), was extended to include SC dosing by incorporating the absorption components of the adult SC PK model [GSK Document Number [2015N263802_01](#)]. The resulting model was used to simulate the three dose groups for 200 mg SC: (1) Q2W for <30 kg; (2) Q10d for \geq 30 kg and <50 kg; (3) QW for \geq 50 kg subjects. The simulations sampled a pediatric population biased towards females (90%) which is typical of an SLE population. Body size parameters (body weight and BMI) were sampled from the NHANES 2015-2016 database and restricted to pediatric subjects between the ages of 5 and 18 years. Other covariates which form model input parameters were sampled from the pediatric study BEL114055 dataset.

For the proposed dosing regimen, the range of exposures in the three dose groups (Q2W <30kg, Q10d \geq 30 to <50kg, QW \geq 50kg) are very similar ([Figure 1](#), [Table 1](#)). At the 30

kg threshold exposure is predicted to be ~15% below and above the target concentration, namely 88 µg/mL (Q2W) and 123 µg/mL (Q10d) relative to the 104 µg/mL target. Similarly, at the 50 kg threshold subjects receiving belimumab Q10d also have exposures 15% below the target value (90 µg/mL vs 104 µg/mL target). For 50 kg subjects receiving QW dosing the exposure is a little higher, predicted to be ~25% above the target (129 µg/mL vs 104 µg/mL target). However, this specific value represents the largest deviation from the target along the exposure-weight relationship for body weights >15 kg (the cut-off weight for enrolment) and does not constitute an “over-exposure” considering the much larger between-subject variability not explained by body weight. In addition, several adults weighed less than 50 kg, similar to pediatrics, and were not considered to have unjustifiably large exposures even though the adults received 200 mg QW.

The exposures across the three dose groups are generally centred about the target value (104 µg/mL), with almost identical between subject variability at steady state ([Figure 2](#)). Additionally, the variability in the average exposure in any of the three dose groups, as expressed by the 90% prediction interval (light grey region, [Figure 1](#)), does not fall outside the range of exposures observed in adults (blue points, [Figure 1](#)). As a result, since no exposure-response relationship for safety was apparent in the adult SC population analysis, or in the pediatric IV study BEL114055, no safety concerns are expected in any of the three dose groups based on the PK predicted for pediatrics.

In summary, belimumab PK in pediatrics is predicted to be very similar across the three dose groups. Within each group, steady state concentrations are centred on the target value (104 µg/mL), between-subject variability is consistent with observed adult data, and deviations from the target exposure are within acceptable limits ($\leq 25\%$ at the body weight thresholds). Therefore, the three-tier dosing regimen, with Q2W dosing for subjects <30 kg, Q10d dosing for subjects between 30 and <50 kg, and QW dosing for subjects ≥ 50 kg is considered appropriate for study 200908.

Figure 1 Average serum concentrations at steady state versus body weight.

Pediatric predictions for the median (solid black line), inter-quartile range (dark grey shaded region) and 90% prediction interval (light grey shaded area) are compared with the post-hoc adult estimates (blue points) and the population adult estimate (broken red, 104 $\mu\text{g/mL}$). The median pediatric concentrations at the 30 kg and 50 kg body weight thresholds are shown (red diamonds 88 and 123 $\mu\text{g/mL}$ at 30 kg, 90 and 129 $\mu\text{g/mL}$ at 50 kg).

[figure not shown]
Table 1 Average serum concentrations at steady state as a function of body weight.

Regimen	Dose	Body Weight (kg)	Serum Concentration ($\mu\text{g/mL}$)
30/50 kg body weight threshold ^a	Q2W <30kg	30	88
	Q10d 30-50 kg	30	123
		50	90
	QW \geq 50 kg	50	129
Adults	QW	67	104 ^b

a. 1-week dosing period switches to 1 dose every 10-days at 50 kg and then to 1 dose every 2-weeks at 30 kg.

b. Estimate based on population parameters from the adult population PK model for SC belimumab administration.

Figure 2 Time course profiles for the three dose groups defined by 30 kg and 50 kg weight thresholds.

Pediatric predictions for the median (solid black line), inter-quartile range (dark grey shaded region) and 90% prediction interval (light grey shaded area) are compared with the population adult estimate (broken red, 104 $\mu\text{g/mL}$).

4.4. End of Study Definition

A participant is considered to have completed the primary study if he/she has completed Part A and Part B of the study up to and including the Week 52 visit. Participants who elect not to join the optional Part B will be considered to have completed Part A of the study if all visits up to Week 11/12 (Day 81-85) are completed. Eligible participants who complete Part B may be enrolled into the optional access extension phase of the study from Week 52 (Section [6.7.1](#)).

The end of the study is defined as the date of the last assessment (16-week post-treatment follow-up) of the last participant in the optional access extension phase.

5. STUDY POPULATION

Prospective approval of protocol deviations to eligibility criteria, also known as protocol waivers or exemptions, is not permitted.

5.1. Inclusion Criteria

Participants are eligible to be included in Parts A and B of the study only if all of the following criteria apply:

Age

1. Participant must be between 5 and 17 years of age inclusive, at the time of Day 1.

Type of Participant and Disease Characteristics

2. Participants who meet the 1997 American College of Rheumatology (ACR) criteria for the classification of SLE ([Appendix 8](#))
 - a. Have or have had in series 4 or more of the 11 ACR criteria for the classification of SLE
3. Have active SLE disease defined as a SELENA SLEDAI score ≥ 6 at screening ([Appendix 9](#)).
4. Have documented positive autoantibody test results within the study screening period, defined as an ANA titre $\geq 1:80$ and/or a positive anti-dsDNA (≥ 30 IU/mL) serum antibody test based on EITHER the study's central laboratory results OR the local laboratory results. Only unequivocally positive values as defined in the laboratory's reference range are acceptable; borderline values will not be accepted.
5. Are on a stable SLE treatment regimen.

“Stable treatment at baseline” consists of any of the following medications (alone or in combination) administered for a period of at least 30 days prior to Day 1:

- Corticosteroids (prednisone or prednisone equivalent up to 0.5 mg/kg/day):

- For those participants on alternating day doses of steroids, use the average of 2 daily doses to calculate the average daily steroid dose.
- Other immunosuppressive or immunomodulatory agents including methotrexate, azathioprine, leflunomide, mycophenolate (including mycophenolate mofetil, mycophenolate mofetil hydrochloride, and mycophenolate sodium), calcineurin inhibitors (e.g. tacrolimus, cyclosporine), sirolimus, oral cyclophosphamide, 6-mercaptopurine or thalidomide.
- Anti-malarials (e.g. hydroxychloroquine, chloroquine, quinacrine)
- Non-steroidal anti-inflammatory drugs (NSAIDs)
- New SLE therapy must not be added within 30 days of Day 1.

Weight

6. Body weight \geq 15 kg.

Sex

7. Male and/or female

Contraceptive use by men or women should be consistent with local regulations regarding the methods of contraception for those participating in clinical studies.

Male Participants

No contraceptive measures are required for male participants.

Female participants:

A female participant is eligible to participate if she is not pregnant or breastfeeding, and at least one of the following conditions applies:

- Is not a woman of childbearing potential (WOCBP) (See [Appendix 4](#))

OR
- Is a WOCBP and is using a contraceptive method that is highly effective, with a failure rate of <1%, as described in [Appendix 4](#) during the belimumab treatment period and for at least 16 weeks, corresponding to the time needed to eliminate any study intervention(s) (e.g., 5 terminal half-lives), after the last dose of study intervention. The investigator should evaluate the effectiveness of the contraceptive method in relationship to the first dose of study intervention.
- A WOCBP must have a negative highly sensitive [[Appendix 2](#)] pregnancy test (serum or as required by local regulations) within 35 days before the first dose of belimumab.
- The investigator is responsible for review of medical history, menstrual history, and recent sexual activity to decrease the risk for inclusion of a woman with an early undetected pregnancy.

Informed Consent

8. Participant signs and dates a written age appropriate assent form (in accordance with applicable regulations) and the parent or legal guardian (or emancipated minor) that has the ability to understand the requirements of the study, provides written informed consent (including consent for the use and disclosure of research-related health information) that the participant will comply with the study protocol procedures (including required study visits).

5.2. Exclusion Criteria

Participants are excluded from Parts A and B of the study if any of the following criteria apply:

Medical Conditions

1. Have an estimated glomerular filtration rate (eGFR) as calculated by Schwartz Formula [[Schwartz](#), 2009] of less than 30 mL/min.
2. Have acute severe nephritis defined as significant renal disease (e.g., the presence of urinary sediments and other lab abnormalities) that, in the opinion of the study investigator, may lead to the participant requiring induction therapy during the first 12 weeks of the trial.

Note: Clinically stable lupus nephritis which can be managed with medications allowed in the study will not exclude participants from participating in the trial (nor will any maximum level of proteinuria exclude participants). Clinical assessment and medical management of nephritis will be at the discretion of the study investigator.

3. Have a history of a major organ transplant (e.g., heart, lung, kidney, liver) or hematopoietic stem cell/marrow transplant.
4. Have clinical evidence of significant, unstable or uncontrolled, acute or chronic diseases not due to SLE (i.e., cardiovascular, pulmonary, hematologic, gastrointestinal, hepatic, renal, neurological, malignancy or infectious diseases) which, in the opinion of the investigator, could confound the results of the study or put the participant at undue risk.
5. Have a planned surgical procedure or a history of any other medical disease (e.g., cardiopulmonary), laboratory abnormality, or condition (e.g., poor venous access) that, in the opinion of the investigator, makes the participant unsuitable for the study.
6. Have a history of malignant neoplasm within the last 5 years.
7. Have evidence of serious suicide risk including any history of suicidal behavior in the last 6 months, or who in the investigator's opinion, pose a significant suicide risk.
8. Have a history of a primary immunodeficiency.

9. Have an IgA deficiency (IgA level <10 mg/dL).
10. Have acute or chronic infections requiring management, as follows:
 - Currently on any suppressive therapy for a chronic infection (such as tuberculosis, pneumocystis, cytomegalovirus, herpes simplex virus, herpes zoster and atypical mycobacteria).
 - Use of parenteral (IV or IM) antibiotics (antibacterials, antivirals, anti-fungals, or anti-parasitic agents) for infection within 60 days of Day 1.
11. Have a Grade 3 or greater laboratory abnormality based on the protocol defined Adverse Event and Laboratory Value Severity Grade scale ([Appendix 2](#), Section [10.2.1](#)) except for the following that are allowed:
 - Stable Grade 3 prothrombin time (PT) secondary to warfarin treatment.
 - Stable Grade 3 partial thromboplastin time (PTT) due to lupus anticoagulant and not related to liver disease or anti-coagulant therapy.
 - Stable Grade 3 hypoalbuminemia due to lupus nephritis, and not related to liver disease or malnutrition.
 - Any grade proteinuria.
 - Stable Grade 3 gamma glutamyl transferase (GGT) elevation due to lupus hepatitis, and not related to alcoholic liver disease, uncontrolled diabetes or viral hepatitis. If present, any abnormalities in the ALT and or AST must be \leq Grade 2.
 - Stable Grade 3 neutropenia; or stable Grade 3 lymphopenia; or stable Grade 3 leukopenia, due to SLE.
12. Have a history of an anaphylactic reaction to parenteral administration of contrast agents, human or murine proteins or monoclonal antibodies or to any of the excipients of the study drug.

Prior/Concomitant Therapy

13. Have ever received treatment with belimumab (BENLYSTA).
14. Have received any of the following within 364 days of Day 1:
 - Treatment with any B-cell targeted therapy (e.g., rituximab, other anti-CD20 agents, anti-CD22 [epratuzumab], anti-CD52 [alemtuzumab], BLyS-receptor fusion protein [BR3], TACI-Fc)
 - Abatacept.
 - Any biologic investigational agent
15. Have required 3 or more courses of systemic corticosteroids for concomitant conditions (e.g., asthma, atopic dermatitis) within 90 days of Day 1 (topical or inhaled steroids are permitted).
16. Have received any of the following within 90 days of Day 1:

- Anti-TNF therapy (e.g., adalimumab, etanercept, infliximab).
- Interleukin-1 receptor antagonist (anakinra).
- Intravenous immunoglobulin (IVIG).
- Plasmapheresis.

17. Have received any of the following within 30 days of Day 1:

- Intravenous (IV) cyclophosphamide.
- A non-biologic investigational agent (30 day window OR 5 half-lives, whichever is greater).
- Any new immunosuppressive/immunomodulatory agent.
- High dose prednisone or equivalent (>1.5 mg/kg/day) or any intramuscular or intravenous steroid injection.
- Note: New inhaled steroids, intraarticular steroids, and new topical immunosuppressive agents (e.g., eye drops, topical creams) are allowed. Any NSAID use for < 1 week is allowed.

18. Have received a live or live-attenuated vaccine within 30 days of Day 1.

19. Have active central nervous system (CNS) lupus (including seizures, psychosis, organic brain syndrome, cerebrovascular accident [CVA], cerebritis or CNS vasculitis) requiring therapeutic intervention within 60 days of Day 1.

20. Have required renal replacement therapy (e.g. hemodialysis, peritoneal dialysis) within 90 days of Day 1 or are currently on renal replacement therapy.

Prior/Concurrent Clinical Study Experience

21. Participation in an interventional clinical study either concurrently or within 6 months of screening. Participation in an observational study may be permitted.

Diagnostic assessments

22. Positive immunodeficiency virus (HIV) antibody test.

23. Hepatitis B: Serologic evidence of Hepatitis B (HB) infection defined as Hepatitis B surface antigen positive (HBsAg+) OR Hepatitis B core antibody positive (HBcAb+).

24. Hepatitis C: Positive test for Hepatitis C antibody confirmed on an additional blood sample by RNA PCR assay. Participants who are positive for Hepatitis C antibody and negative when the Hepatitis C RNA-PCR assay is performed on an additional sample will be eligible to participate. Participants who are positive for Hepatitis C antibody and have a positive result for the HCV when the Hepatitis C RNA PCR assay is performed on the additional sample will not be eligible to participate. (Institution or country specific guidelines for blood sample volume limits must be followed in collection of the additional blood sample.)

Other Exclusions

25. Have current drug or alcohol abuse or dependence, or a history of drug or alcohol abuse or dependence within 364 days prior to Day 1.
26. Are unable or unlikely, in the opinion of the investigator, to administer belimumab by SC injection and have no reliable source to administer the injection.
27. Children in Care: A Child in Care (CiC) is a child who has been placed under the control or protection of an agency, organisation, institution or entity by the courts, the government or a government body, acting in accordance with powers conferred on them by law or regulation. The definition of a CiC can include a child cared for by foster parents or living in a care home or institution, provided that the arrangement falls within the definition above. The determination of whether a child meets the definition of CiC should be made with the study centre staff in consultation with the responsible IRB/Ethics Committee.

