Hypokalemia	3.0-3.4 meq/L	2.5-2.9 meq/L	2.0-2.4 meq/L	< 2.0 meq/L
Hyperkalemia	5.6-6.0 meq/L	6.1-6.5 meq/L	6.6-7.0 meq/L	> 7.0 meq/L
Phosphate				
Hypophosphatemia	2.0-2.4 mg/dL	1.5-1.9 mg/dL	1.0-1.4 mg/dL	< 1.0 mg/dL
Calcium- (Corrected For Albumin)				
Hypocalcemia	7.8-8.4 mg/dL	7.0-7.7 mg/dL	6.1-6.9 mg/dL	< 6.1 mg/dL
Hypercalcemia	10.6-11.5 mg/dL	11.6-12.5 mg/dL	12.6-13.5 mg/dL	>13.5 mg/dL
Magnesium				
Hypomagnesemia	1.2-1.4 meq/L	0.9-1.1 meq/L	0.6-0.8 meq/L	< 0.6 meq/L
Albumin				
Hypoalbuminemia	3.00-3.49 g/dL	2.50-2.99 g/dL	2.00-2.49 g/dL	< 2.00 g/dL
Bilirubin (Total)				
Hyperbilirubinemia (Total)	> 1.0-1.5 x ULN	> 1.5-2.5 x ULN	> 2.5-5 x ULN	> 5 x ULN
Glucose				
Hypoglycemia	55-64 mg/dL	40-54 mg/dL	30-39 mg/dL	< 30 mg/dL
Hyperglycemia (nonfasting & no prior diabetes)	116-160 mg/dL	161-250 mg/dL	251-500 mg/dL	> 500 mg/dL
Triglycerides	151-399 mg/dL	400-750 mg/dL	751-1200 mg/dL	> 1200 mg/dL
Creatinine	> 1.0-1.5 x ULN	> 1.5-3.0 x ULN	> 3.0-6.0 x ULN	> 6.0 x ULN

Adverse Event and Laboratory Value Severity Grade Table (continued)

	GRADE 1 MILD	GRADE 2 MODERATE	GRADE 3 SEVERE	GRADE 4 POTENTIALLY LIFE-THREATENING
CHEMISTRIES (continued)				
Uric Acid				
Hyperuricemia	7.5-10.0 mg/dL	10.1-12.0 mg/dL	12.1-15.0 mg/dL	> 15.0 mg/dL
Liver Transferases (AST, ALT, and GGT)	1.25-2.5 x ULN	> 2.5-5.0 x ULN	> 5.0-10.0 x ULN	> 10.0 x ULN
Alkaline Phosphatase	1.25-2.5 x ULN	> 2.5-5.0 x ULN	> 5.0-10.0 x ULN	> 10.0 x ULN
Pancreatic Enzymes				
Amylase	> 1.0-1.5 x ULN	> 1.5-2.0 x ULN	> 2.0-5.0 x ULN	> 5.0 x ULN
Pancreatic amylase	> 1.0-1.5 x ULN	> 1.5-2.0 x ULN	> 2.0-5.0 x ULN	> 5.0 x ULN
Lipase	> 1.0-1.5 x ULN	> 1.5-2.0 x ULN	> 2.0-5.0 x ULN	> 5.0 x ULN
Hypoglobulinemia (IgG)*	550-700 mg/dL	400-549 mg/dL	250-399 mg/dL	< 250 mg/dL

(continued)

*[Eibl, 1995; Goldfarb, 2001; Yamani, 2001].

Adverse Event and Laboratory Value Severity Grade Table (continued)

GASTROINTESTINAL	GRADE 1 MILD	GRADE 2 MODERATE	GRADE 3 SEVERE	GRADE 4 POTENTIALLY LIFE- THREATENING
Nausea	Mild OR transient; reasonable intake maintained	Mod discomfort OR intake decreased for < 3 days	Severe discomfort OR minimal intake for ≥ 3 days	Hospitalization required

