- Any female participant who becomes pregnant while participating will discontinue study intervention and be withdrawn from the study.
- Investigator will collect pregnancy information on any female participant, who becomes pregnant while participating in this study.
- Information will be recorded on the appropriate form and submitted to GSK within 24 hours of learning of a participant's pregnancy.
- Participant will be followed to determine the outcome of the pregnancy. The investigator will collect follow-up information on participant and neonate, which will be forwarded to GSK. Generally, follow-up will not be required for longer than 6 to 8 weeks beyond the estimated delivery date.
- Any termination of pregnancy will be reported, regardless of fetal status (presence or absence of anomalies) or indication for procedure.
- While pregnancy itself is not considered to be an AE or SAE, any pregnancy complication or elective termination of a pregnancy for a medical reason will be reported as an AE or SAE.
- A spontaneous abortion is always considered to be an SAE and will be reported as such.
- Any SAE occurring as a result of a post-study pregnancy which is considered reasonably related to the study intervention by the investigator, will be reported to GSK as described in [Appendix 3](#). While the investigator is not obligated to actively seek this information in former study participants, he or she may learn of an SAE through spontaneous reporting.

10.5. Appendix 5 Liver Safety: Required Actions and Follow-up Assessments and Study Intervention Restart Guidelines

Phase III-IV liver chemistry stopping and increased monitoring criteria have been designed to assure participant safety and evaluate liver event etiology

Phase III-IV liver chemistry stopping criteria and required follow-up assessments

Liver Chemistry Stopping Criteria	
ALT-absolute	ALT \geq 8xULN
ALT Increase	ALT \geq 5xULN but <8 xULN persists for ≥ 2 weeks ALT \geq 3xULN but <5 xULN persists for ≥ 4 weeks
Bilirubin^{1, 2}	ALT \geq 3xULN and bilirubin \geq 2xULN ($>35\%$ direct bilirubin)
INR²	ALT \geq 3xULN and INR >1.5
Cannot Monitor	ALT \geq 5xULN but <8 xULN and cannot be monitored weekly for ≥ 2 weeks ALT \geq 3xULN but <5 xULN and cannot be monitored weekly for ≥ 4 weeks
Symptomatic³	ALT \geq 3xULN associated with symptoms (new or worsening) believed to be related to liver injury or hypersensitivity
Required Actions and Follow-up Assessments	
Actions	Follow-Up Assessments

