
 • Immediately discontinue study intervention • Report the event to GSK within 24 hours • Complete the liver event CRF and complete an SAE data collection tool if the event also meets the criteria for an SAE² • Perform liver event follow-up assessments • Monitor the participant until liver chemistries resolve, stabilize, or return to within baseline (see MONITORING below) • Do not restart participant with study treatment. Permanently discontinue study intervention and continue participant in the study for any protocol specified follow-up assessments. 	
 • Viral hepatitis serology⁴ • Obtain INR and recheck with each liver chemistry assessment until the transaminases values show downward trend • Only in those with underlying chronic Hepatitis B at study entry (identified by positive Hepatitis B surface antigen) quantitative Hepatitis B DNA and Hepatitis delta antibody⁵. • Obtain blood sample for pharmacokinetic (PK) analysis, within 6 weeks after last dose⁶ • Serum creatine phosphokinase (CPK) and lactate dehydrogenase (LDH).

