
MONITORING:
 
For bilirubin or INR criteria:
 
 Repeat liver chemistries (include ALT, AST, alkaline phosphatase, bilirubin and INR) and perform liver event follow-up assessments within 24 hrs Monitor participants twice weekly until liver chemistries resolve, stabilize or return to within baseline A specialist or hepatology consultation is recommended 
For All other criteria:
 
 Repeat liver chemistries (include ALT, AST, alkaline phosphatase, bilirubin and INR) and perform liver event follow-up assessments within 24-72 hrs Monitor participants weekly until liver chemistries resolve, stabilize or return to within baseline 	
 Fractionate bilirubin, if total bilirubin $\geq 2 \times \text{ULN}$ Obtain complete blood count with differential to assess eosinophilia Record the appearance or worsening of clinical symptoms of liver injury, or hypersensitivity, on the AE report form Record use of concomitant medications on the concomitant medications report form including acetaminophen, herbal remedies, other over the counter medications. Record alcohol use on the liver event alcohol intake case report form (CRF) page 
For bilirubin or INR criteria:
 
 Anti-nuclear antibody, anti-smooth muscle antibody, Type 1 anti-liver kidney microsomal antibodies, and quantitative total immunoglobulin G (IgG) or gamma globulins. Serum acetaminophen adduct high performance liquid chromatography (HPLC) assay (quantifies potential acetaminophen contribution to liver injury in participants with definite or likely acetaminophen use in the preceding week [James, 2009]). NOTE: not required in China Liver imaging (ultrasound, magnetic resonance, or computerised tomography) and /or liver biopsy to evaluate liver disease: complete Liver Imaging and/or Liver Biopsy CRF forms.
---	---

1. Serum bilirubin fractionation should be performed if testing is available. If serum bilirubin fractionation is not immediately available, discontinue study intervention for that participant if $\text{ALT} \geq 3 \times \text{ULN}$ **and** bilirubin $\geq 2 \times \text{ULN}$. Additionally, if serum bilirubin fractionation testing is unavailable, **record presence of detectable urinary bilirubin on dipstick**, indicating direct bilirubin elevations and suggesting liver injury.

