
ALT \geq5xULN and $<$8xULN and bilirubin $<$2xULN without symptoms believed to be related to liver injury or hypersensitivity, and who can be monitored weekly for 2 weeks.
 
OR
 
ALT \geq3xULN and $<$5xULN and bilirubin $<$2xULN without symptoms believed to be related to liver injury or hypersensitivity, and who can be monitored weekly for 4 weeks.
	
 • Notify the GSK medical monitor within 24 hours of learning of the abnormality to discuss participant safety. • Participant can continue study intervention • Participant must return weekly for repeat liver chemistries (ALT, AST, alkaline phosphatase, bilirubin) until they resolve, stabilise or return to within baseline • If at any time participant meets the liver chemistry stopping criteria, proceed as described above • If ALT decreases from ALT \geq5xULN and $<$8xULN to \geq3xULN but $<$5xULN, continue to monitor liver chemistries weekly. • If, after 4 weeks of monitoring, ALT $<$3xULN and bilirubin $<$2xULN, monitor participants twice monthly until liver chemistries normalize or return to within baseline.

References

Le Gal F, Gordien E, Affolabi D, Hanslik T, Alloui C, Dény P, et al. Quantification of hepatitis delta virus RNA in serum by consensus real-time PCR indicates different

patterns of virological response to interferon therapy in chronically infected subjects.
J Clin Microbiol. 2005;43(5):2363–2369.

10.5.1. Restart Following Transient Resolving Liver Stopping Events Not Related to Study Intervention

After liver stopping criteria are met, restart or rechallenge is not permitted, see Section 7.1.2.1.

10.6. Appendix 6: Medical Device Incidents: Definition and Procedures for Recording, Evaluating, Follow-up, and Reporting

Definition and Documentation of Medical Device Incidents

Definitions of a Medical Device Incident

The detection and documentation procedures described in this protocol apply to all GSK medical devices provided for use in the study (see Section 6.1 for the list of GSK medical devices).

Medical Device Incident Definition

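### Exclusion 11 admits a child whose pre-dose ALT and bilirubin already meet Appendix 5's immediate, permanent stopping rule

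*Protocol*

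**What the plan says.** **Entry.** Criterion 11 (Protocol Section 5.2) excludes children who "Have a Grade 3 or greater laboratory abnormality based on the protocol defined Adverse Event and Laboratory Value Severity Grade scale", with listed exceptions. The GGT exception, for stable Grade 3 elevation from lupus hepatitis, says that "any abnormalities in the ALT and or AST must be" no worse than Grade 2. In the severity table (Section 10.2.1), the row beginning "Liver Transferases (AST, ALT, and GGT" sets Grade 2 at >2.5 to 5.0 x ULN. Total bilirubin is Grade 2 at >1.5 to 2.5 x ULN. Criterion 5 also lets a child be refused for any "laboratory abnormality, or condition (e.g., poor venous access) that, in the opinion of the investigator, makes the participant unsuitable for the study". Criterion 4 is a similar judgement on significant uncontrolled disease not due to SLE, hepatic disease included. Neither gives a liver threshold.

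**Stopping.** Appendix 5 (Section 10.5), under "Phase III-IV liver chemistry stopping criteria and required follow-up assessments", lists eight conditions. One is ALT >=3 x ULN with bilirubin >=2 x ULN and more than 35% direct. Footnote 1 drops the direct-fraction condition when it cannot be checked: "If serum bilirubin fractionation is not immediately available, discontinue study intervention for that participant if" ALT and bilirubin reach those multiples. Another is ALT of 3 to <5 x ULN lasting at least 4 weeks. The required action is: "Permanently discontinue study intervention and continue participant in the study for any protocol specified follow-up assessments". Section 7.1.2.1 forbids restart, and Section 7.1 adds withdrawal from the study.

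**Monitoring.** A second table lets dosing continue under weekly tests for ALT of 3 to <8 x ULN with bilirubin <2 x ULN and no symptoms. It gives way to the first: "If at any time participant meets the liver chemistry stopping criteria, proceed as described above".

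**The concern.** Entry limits and stop limits should not overlap. Here a site can confirm that a child is eligible while the same results meet a criterion for taking that child off drug for good. The pair involved, ALT >=3 x ULN with bilirubin >=2 x ULN, is also what Appendix 5 flags as possible severe liver injury and requires to be reported as an SAE. In a single-arm study, a stop and an SAE that arise from values present before the first dose are hard to tell apart from a drug effect.

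Three things are at stake: a child exposed to drug with a foreseeable permanent stop, a blurred liver-safety signal, and possibly the loss of that child's observed Week 12 concentration, which is a primary endpoint.

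**Working it through.** The plan gives no figure for this overlap, so the check sets the two sets of limits side by side and then follows the calendar.

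**1. Overlap (x ULN)**

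| | Highest eligible (Grade 2) | Stop threshold | Eligible and stoppable |
|---|---|---|---|
| ALT with bilirubin | ALT 5.0, bilirubin 2.5 | ALT >=3 and bilirubin >=2 (>35% direct or unfractionated) | ALT 3.0-5.0 with bilirubin 2.0-2.5 |
| ALT alone | 5.0 | 3 to <5 for >=4 weeks | 3.0 to <5 |

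ALT of exactly 5.0 is still Grade 2 and falls under the 2-week rule for 5 to <8 x ULN. ALT below 3 x ULN meets none of the eight conditions, whatever the bilirubin.

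**2. The pair.** No persistence is needed. Chemistry is scheduled at screening and Day 1 (Protocol Section 1.3), so an unchanged pair is visible then. Suppose the Day 1 result returns after dosing and only that dose was given. The liver-event PK sample is due within 6 weeks of the last dose, so by 1 + 42 = Day 43. The SAP Section 13.1.1 window for Week 12 opens on Day 71, so this sample does not reach it.

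**3. ALT alone, if a stable value counts.** The protocol does not say when the 4 weeks begin.

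- *From Day 1:* met at 1 + 28 = Day 29, seen at the Day 29 chemistry (Cohorts 1 and 3) or Day 31 (Cohort 2). The early-withdrawal visit is due within 4 weeks of the decision (Section 8.5), so by 29 + 28 = Day 57 or 31 + 28 = Day 59. Both are before Day 71.
- *From the first on-treatment chemistry:* met at 29 + 28 = Day 57 or 31 + 28 = Day 59 (the next scheduled Cohort 2 test is Day 61). The early-withdrawal visit may then be as late as 57 + 28 = Day 85 or 59 + 28 = Day 87. Those lie inside the Week 12 windows (Days 71-98 and 71-96).

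The earliest decision from which an on-time early-withdrawal visit can reach the window is 71 - 28 = Day 43.

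**4. Can a Day 29/31 stop still give a Week 12 value?** If that day's in-clinic dose was given, the 6-week PK sample may be taken as late as 29 + 42 = Day 71 or 31 + 42 = Day 73, the edge of the window. Without that dose, the last doses are Days 22, 21 and 15 in Cohorts 1, 2 and 3. The limits are then Days 64, 63 and 57, all too early. Even a sample at the edge is post-discontinuation, and SAP Section 9.1 summarises scheduled visits with pre-dosing samples, so its inclusion is not assured.

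**5. Dosing before a Day 29/31 stop**

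| Cohort | Due before Week 12 sample | Received, without / with that day's dose |
|---|---|---|
| 1 | 12 (Days 1, 8, ..., 78) | 4 / 5 |
| 2 | 8 (Days 1, 11, ..., 71) | 3 / 4 |
| 3 | 6 (Days 1, 15, ..., 71) | 2 / 3 |

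Three of the five scheduled on-treatment Part A PK samples are already taken.

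**6. Numbers.** The documents give no frequency of ALT >=3 x ULN at entry. As a pure assumption, let a proportion p of the 28 enrolled have it. The expected number is 28p and the chance of at least one is 1 - (1 - p)^28.

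| p | Expected | At least one |
|---|---|---|
| 1% | 0.28 | 25% |
| 3% | 0.84 | 57% |
| 5% | 1.40 | 76% |

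The ALT-bilirubin pair would be rarer than isolated ALT elevation. The plan allows for 28 - 24 = 4 non-evaluable participants.

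**The case against.** A reader might infer that any child whose ALT stays at 3 to 5 x ULN must come off drug before Week 12. The documents do not support that. The persistence rows are labelled *ALT Increase*, in contrast to *ALT-absolute* for >=8 x ULN, so an unchanged value is arguably not covered. Section 7.1.2 refers the decision to Algorithms A and B, which are figures not shown and could contain a baseline provision. The word baseline does occur in Appendix 5, though only to say when monitoring ends or is reduced; no stop threshold uses it.

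Nor does bilirubin of 2.0 to 2.5 x ULN stop anyone by itself. SAP Table 5 lists direct bilirubin, so the unfractionated route may be narrow. Criteria 4 and 5 let an investigator refuse such a child, hepatitis B and C infection and alcohol abuse are already excluded, and a liver monitoring event must reach the Medical Monitor within 24 hours.

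Generous entry with a stricter stop can also be defended as deliberate: the GGT exception knowingly admits stable lupus hepatitis in a rare population.

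Most of this stands for isolated ALT. It does not remove the problem for the pair, whose row carries no persistence condition or *increase* label. The backstops are discretionary, and the monitoring table both requires bilirubin <2 x ULN and yields to the stop rules.

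**Conclusion.** The point holds for the pair: on the readable text, ALT of 3.0 to 5.0 x ULN with bilirubin of 2.0 to 2.5 x ULN (>35% direct or unfractionated) is both eligible and an immediate permanent stop. For isolated ALT of 3 to <5 x ULN, the finding is an ambiguity about stable values and the start of the 4-week clock.

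The matter is minor. The number of children is unknown and probably small. It might be inferred that each one loses the Week 12 concentration. That is likely after an early stop but not certain, because a sample at the edge of the window or a later stop can still be slotted to Week 12. Early samples keep the child in the PK population, and planned precision has wide margin (mean 95% intervals of 83.8-116.2% for clearance and 80.5-119.5% for volume, against limits of 60-140%), so the effect on population PK is small. The conclusion assumes that Algorithms A and B agree with the Appendix 5 tables.

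**What to change.** Add to criterion 11, and repeat in its GGT exception, that ALT >=3 x ULN with total bilirubin >=2 x ULN (>35% direct or unfractionated) on the latest available pre-dose result is exclusionary.

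For isolated ALT of 3 to 5 x ULN, choose one:

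- exclude it as well, which removes the whole overlap for values known before dosing, since all eight stop conditions need ALT >=3 x ULN; or
- state in Appendix 5 how a stable baseline value is treated and when the 4-week clock starts.

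The cost is wording. Chemistry is already drawn at screening and Day 1. There may be a few screen failures beyond the planned 36 - 28 = 8. Excluding isolated ALT >=3 x ULN would also lose some children with stable lupus hepatitis, which is a real trade-off; excluding the pair costs almost nothing.

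Neither change catches a rise first reported after the Day 1 dose. The latest earlier chemistry may be up to 35 days old, and in Cohort 3 is at least 14 days old.

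If enrolment has closed, the sponsor can still state the clock start and identify in the study report any liver stop with baseline ALT >=3 x ULN, using listings L3.13 and L3.25.
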